3.6. STATISTICS

3.6.1. STUDY POPULATIONS

The following populations will be considered for analysis:

- **Intention-to-observe (ITO) population:** All subjects who enrolled in Study ALX0681-C302.
- **Recurrence population:** All subjects in the ITO population who have experienced at least one recurrence in Study ALX0681-C302.

Unless otherwise specified, the ITO population will be used for the analysis of the Q6M FU data on efficacy, disease-related markers, PD, immunogenicity and safety. The recurrence population will be used for analysis of data collected during recurrence periods. Depending on whether subjects have been treated with caplacizumab or not, or have been retreated with caplacizumab, different subsets of the recurrence population may be defined for specific analyses. This will be detailed in the statistical analysis plan (SAP).

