(1) caplacizumab-treated, defined as subjects in the ITO population who have been randomized to caplacizumab in Study ALX0681-C301, evaluated up to their first recurrence⁺⁺⁺; (2) standard of care-treated, defined as subjects in the ITO population who have been randomized to placebo in Study ALX0681-C301, evaluated up to their first recurrence.

All efficacy endpoints related to assessments during the recurrence period will be analyzed using the recurrence population. The effect of retreatment of caplacizumab on these endpoints will be evaluated.

Select sensitivity analyses may be planned to assess the effect of heterogeneity in the timings of the baseline visit between subjects. More details will be provided in the SAP. Unless specified otherwise, no missing data imputation will be applied, and all efficacy endpoints will be analyzed as observed.

3.6.5. EVALUATION OF PHARMACOKINETIC AND PHARMACODYNAMIC, DISEASE RELATED MARKERS AND IMMUNOGENICITY PARAMETERS

Individual study drug concentrations will be listed. In addition a listing of the actual sampling times relative to the study drug administration times will be presented.

Drug concentrations will be summarized by sampling time using descriptive statistics and will be listed and summarized in tabular and/or graphical form.

All PD and disease-related marker data will be summarized using descriptive statistics and will be listed and summarized in tabular and/or graphical form.

Immunogenicity will be assessed through listing of individual (ADA, mADA and nAb) results by subject, summary tables and immunogenicity time profiles. Immunogenicity data will be correlated with PK and PD readout using descriptive statistics per subject category based on pre-Ab and TE ADA status (using ADA results obtained in Study ALX0681-C301), summarized in tabular and/or graphical form. In addition, immunogenicity will be correlated with possible safety findings. The effect of retreatment with caplacizumab on immunogenicity will be assessed.

⁺⁺⁺ Subjects who had a recurrence during Study ALX0681-C301 or between the Final (28 day) FU visit in Study ALX0681-C301 and Screening/Baseline in Study ALX0681-C302, will not be considered for the group-wise analyses.

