2.1.4 Safety endpoints

The safety analysis will be based on the reported adverse events and other safety information, such as clinical laboratory data, vital signs and physical examination.

Observation period

The observation period will be divided into 2 non mutually exclusive periods: the on-study period and the recurrence period.

The on-study observation period is defined as the time from informed consent until the end of the study (defined as last protocol planned visit).

The recurrence period is from the start of the recurrence episode, defined as recurrent thrombocytopenia requiring initiation of daily PE, until the last recurrence follow-up visit of that episode. In case of treatment with the IMP, the recurrence period is divided into 2 epochs:

- the **treatment epoch** is defined as the time from the first administration of the IMP to the last administration of the IMP.
- the **residual treatment** epoch is defined as the time from the last administration of the IMP to the last administration of the IMP + 30 days.

The treatment-emergent adverse event (TEAE) period will include both treatment and residual treatment epochs.

In case treatment with the IMP is not initiated during the recurrence episode, there is no subdivision of the recurrence period into the treatment epoch and the residual treatment epoch. The adverse event occurring during that period are not identified as treatment-emergent adverse events.

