2.4.4 Analyses of efficacy endpoints

All efficacy endpoints related to assessments on the Q6M FU visits will be analyzed using the ITO population. Summarization will be conducted on the total study population and by analysis group. For the group-wise analysis, the following groups will be considered:

- caplacizumab-treated: defined as subjects in the ITO population who have been randomized to caplacizumab in study ALX0681-C301, evaluated up to their first recurrence in the ALX0681-C302 trial;
- standard of care-treated, defined as subjects in the ITO population who have been randomized to placebo in study ALX0681-C301, evaluated up to their first recurrence in the ALX0681-C302 trial.

Subjects who had a recurrence during study ALX0681-C301 or between the Final (28 day) FU visit in study ALX0681-C301 and Screening/Baseline in study ALX0681-C302, will not be considered for the group-wise analyses.

All efficacy endpoints related to assessments during the recurrence period will be analyzed using the recurrence population. The effect of retreatment of caplacizumab on these endpoints will be evaluated. For the group-wise analysis the following groups are considered, unless otherwise specified:

- Treated with IMP: defined as subjects in the recurrence population who received caplacizumab in the ALX0681-C302 during a recurrence episode
- Not treated with IMP: defined as subjects in the recurrence population who did not receive caplacizumab in the ALX0681-C302 during a recurrence episode.

Of note, depending on the recurrence episode, the same subject can appear in both analysis groups.

Select sensitivity analyses may be planned to assess the effect of heterogeneity in the timings of the baseline visit between subjects. Unless specified otherwise, no missing data imputation will be applied, and all efficacy endpoints will be analyzed as observed.

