2.4.5 Analyses of safety data

The summary of safety results will be presented by treatment group. For the ITO population, the treatment groups are:

- Caplacizumab total: Subjects who received caplacizumab during the ALX0681-C301 study (during the double blind or the open-label periods).
- Not treated: Subjects who never received Caplacizumab during the ALX0681-C301 trial

For the recurrence population, adverse events will be presented for:

- Treated with IMP: patients treated with caplacizumab in the ALX0681-C302 study
- Not Treated with IMP: patients not treated with caplacizumab in the ALX0681-C302 study during the trial

General common rules

All safety analyses will be performed on the ITO and recurrence populations as defined in [Section 2.3.2](#), unless otherwise specified, using the following common rules:

- For analysis related to the Q6M FU visits, the baseline value is defined as screening/baseline value visit. For analysis related to the recurrence period, the baseline value is defined as the recurrence visit value and will be calculated for each recurrence period separately
- For assessments with multiple parameters per participant (such as laboratory assessments), baseline will be determined per parameter individually. It is recognized that baseline assessments may thus come from more than one assessment and not just from the “baseline visit” assessment.
- For quantitative safety parameters based on central laboratory/reading measurements, descriptive statistics will be used to summarize results and change from baseline values by visit.
- The analysis of the safety variables will be essentially descriptive, and no systematic testing is planned.

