2.4.5.1 Analyses of adverse events

Generalities

The primary focus of adverse event reporting will be on treatment-emergent adverse events. Pretreatment and posttreatment adverse events will be described separately.

If an adverse event date/time of onset (occurrence, worsening, or becoming serious) is incomplete, an imputation algorithm will be used to classify the adverse event as pretreatment,

treatment-emergent, or posttreatment. The algorithm for imputing date/time of onset will be conservative and will classify an adverse event as treatment emergent unless there is definitive information to determine it is pretreatment or posttreatment. Details on classification of adverse events with missing or partial onset dates are provided in [Section 2.5.3](#).

Adverse events (AEs) will be placed into analysis periods according to their start date (time). The AE will only be presented in the analysis period during which it started, ie, period start date (time) \leq AE start date (time) \leq period stop date (time). There will be no imputation of other missing date (time) fields, nor of the missing parts of other partially known date (time) fields. When needed (e.g., an incomplete date (time) leads to a double phase allocation), the following rules will be applied: adverse events will be allocated on all analysis levels (ie, for analysis periods and subperiods, see [Section 2.5.4](#)) according to their start date (time). In case the adverse event (AE) start date(time) is incomplete, the allocation will be done according to the available parts of the AE start date(time) and taking into account the AE end date(time) (ie, the AE start date(time) cannot be later than the AE end date(time)):

- When, due to missing date (part) an allocation needs to be made to an analysis period, the AE will be allocated to the treatment phase and not off-treatment phase (worst-case allocation).
- When an allocation needs to be made to a specific recurrence period, the AE will be allocated to the first recurrence period.
- When an allocation needs to be made within a recurrence period, the event will be allocated to the daily PE subperiod.

Tables on the recurrence population will include only adverse events that occurred during the recurrence period, treatment-emergent (for patients who received the IMP) and non-treatment emergent (for patients who did not received the IMP).

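### The plan promises to evaluate retreatment, but the SAP's 'Treated with IMP' group pools first and repeat caplacizumab exposure, so no group table shows the effect across C301 and C302

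*SAP*

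**What the plan says.** Repeated use is one of the three study objectives (Protocol 2, SAP 1.2). Immunogenicity of repeated treatment is a main endpoint in the protocol synopsis, and Protocol 1.2.5 calls the risk that retreatment induces anti-drug antibodies (ADA) unknown.

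On analysis, Protocol 3.6.4 states for recurrence-period endpoints: "The effect of retreatment of caplacizumab on these endpoints will be evaluated". Protocol 3.6.5 states: "The effect of retreatment with caplacizumab on immunogenicity will be assessed". Protocol 3.6.1 leaves the detail to the SAP: depending on whether subjects have been treated, "or have been retreated with caplacizumab, different subsets of the recurrence population may be defined for specific analyses".

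SAP 2.4.4 repeats the efficacy commitment and then defines "Treated with IMP: defined as subjects in the recurrence population who received caplacizumab in the ALX0681-C302 during a recurrence episode". SAP 2.4.5 (adverse events) and 2.4.5.5.5 (immunogenicity) also define the treated recurrence group by C302 receipt, the latter for the specific episode. The subgroups in SAP 2.4.4.9.1 use ADAMTS13 activity and the number of C301 recurrences.

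For the ITO safety and six-monthly immunogenicity tables the comparison column is "Not treated: Subjects who never received Caplacizumab during the ALX0681-C301 trial". On the period: "The on-study observation period is defined as the time from informed consent until the end of the study".

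**The concern.** Patients from both C301 arms enter C302, and a recurrence is treated with open-label caplacizumab whatever the C301 arm, provided the treatment criteria are met (Protocol 3.1.2, 3.2.3, 3.3.1). The treated recurrence group therefore holds two kinds of patient. One was on placebo throughout C301 and now receives the drug for the first time. The other received it in C301, double-blind or after crossover to open label, and is being retreated.

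The retreatment question is how the second kind compares with the first. With both in one column, the repeated-use objective cannot be read from the group tables for efficacy, treatment-emergent adverse events (TEAEs) or immunogenicity. The loss is greatest for ADA: antibody carried over from C301 and antibody first induced in C302 can sit in the same column.

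**Working it through.** **1. The group definitions side by side**

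| Analysis | SAP section | Group defined by | Uses both studies? |
|---|---|---|---|
| ITO efficacy | 2.4.4 | C301 randomised arm, followed to first C302 recurrence | No |
| Recurrence efficacy | 2.4.4 | Receipt in C302 | No |
| ITO safety | 2.4.5 | Receipt in C301 | No |
| Recurrence safety | 2.4.5 | Receipt in C302 | No |
| Six-monthly immunogenicity | 2.4.5.5.5 | Receipt in C301 | No |
| Recurrence immunogenicity | 2.4.5.5.5 | Receipt in C302, that episode | No |
| Subgroups | 2.4.4.9.1 | ADAMTS13 activity; number of C301 recurrences | Neither is exposure |

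No row crosses C301 exposure with C302 exposure.

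**2. Size of the two strata (illustration)**

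The documents do not give the number of placebo patients treated in C302. Inputs, all from the protocol:
- 92 patients randomised 1:1 in C301 (1.2.4), so 46 on placebo; all are assumed to enrol, which is an upper bound.
- Placebo crossover to open-label drug in C301 from 0 to 33.3%. The upper figure is the Phase II placebo proportion with exacerbation and/or relapse (1.2.4).
- Recurrence of 18% (median) or 3% (low end) from 1.1, assumed equal in both strata. The 84% end comes from a study with 13 years' mean follow-up and is not used.
- Every recurrence treated, counting each patient's first treated C302 recurrence.

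First exposure = 46 × (1 − crossover) × recurrence.
Repeat exposure = (46 + 46 × crossover) × recurrence.

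- 18%, crossover 0: 46 × 0.18 = 8.3 first; 46 × 0.18 = 8.3 repeat.
- 18%, crossover 33.3%: 30.7 × 0.18 = 5.5 first; 61.3 × 0.18 = 11.0 repeat.
- 3%, crossover 0: 1.4 first; 1.4 repeat.
- 3%, crossover 33.3%: 0.9 first; 1.8 repeat.

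First exposures are 46/92 = 50% down to 30.7/92 = 33% of the pooled group. Under equal recurrence this share does not depend on the recurrence rate. The counts scale with it, so they would be larger above 18%.

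**3. Drug time inside the ITO columns**

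Daily plasma exchange is taken as 5.9 days (Phase II caplacizumab mean, Protocol 1.2.4).
- Treatment: 5.9 + 30 = about 36 days; with the full 28-day extension, about 64 days.
- With the 30-day residual epoch (SAP 2.1.4): about 66 to 94 days.
- Share of 3 years (1,095 days) at 18% recurrence, one each: 36/1,095 × 0.18 = 0.6% to 64/1,095 × 0.18 = 1.05%. With the residual epoch, 1.1% to 1.5%.

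**The case against.** **Partial information exists.** The SAP summarises several recurrence outcomes by episode: TTP-related and thromboembolic events, presenting symptoms, duration, outcome, days of daily plasma exchange, and hospital and ICU days (2.4.4.1, 2.4.4.2, 2.4.4.4, 2.4.4.5.2, 2.4.4.5.3). Immunogenicity is listed and plotted by patient (2.4.5.5.5). This stands, and repeat treatment within C302 is partly visible. But episode 1 still mixes first exposure with re-exposure after C301, time to platelet count (2.4.4.5.1) has no stated per-episode summary, and listings are not a group summary.

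**Protocol 3.6.1 is permissive.** It says subsets may be defined, so their absence breaches nothing there. This also stands. The point rests on the firm commitments in Protocol 3.6.4 and 3.6.5 and SAP 2.4.4.

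**Cells will be small.** SAP 2.4.4.9.1 itself requires at least 5 participants per subgroup category. The 5.5 first exposures at 33.3% crossover fall below 5 once enrolment drops under about 91% (5/5.5). This limits the form of the output, but does not justify pooling in a study without formal tests.

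**A stronger reading of the ITO tables.** A reader might infer that the 'Not treated' column is biased because patients first dosed in C302 stay in it. The documents do not support that. The label is explicitly tied to C301, and C302 drug enters both columns. Treatment occupies about 1% of follow-up in the illustration. TEAEs are tabulated in the recurrence population, and the ITO efficacy groups stop at first recurrence. SAP 2.4.5.1 adds "Pretreatment and posttreatment adverse events will be described separately", although it gives the ITO tables only one period. A drug-induced ADA in such a patient can be traced through the modified ADA assay and the listings. What remains is labelling.

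**Conclusion.** The point holds and should be fixed. Followed exactly, the SAP's groups leave the effect of retreatment across C301 and C302 unshown in any planned group table, despite a stated objective, a main endpoint and explicit commitments to evaluate it. Because the analysis is descriptive (SAP 2.4.4.8), the consequence is for interpretation; no error rate or power is involved. The stratum sizes, about 6 to 8 first and 8 to 11 repeat at 18% recurrence and about 1 and 1 to 2 at 3%, rest on the assumptions listed and are not estimates of what C302 observed.

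The 'Not treated' column is a minor labelling matter, and no bias is claimed. A reader might also infer that the pre-dose reference for the two neutralising-antibody assays must change for patients first exposed in C302. It need not: for anyone untreated in C301, the C302 baseline visit already precedes any trial caplacizumab. The ADA, modified ADA and overall classes do not use a pre-dose reference at all (SAP 2.4.5.5.2).

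One point needs clarification. Protocol 3.6.5 bases the PK and PD correlation on categories "per subject category based on pre-Ab and TE ADA status (using ADA results obtained in Study ALX0681-C301"; the SAP does not say whether C301 results are used.

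**What to change.** 1. For each C302 recurrence episode, derive a prior-caplacizumab flag: any dose in C301 (double-blind or open-label) or in an earlier C302 episode. Subject identifiers are linked across the studies (Protocol 3.4.1.1), and the SAP already needs C301 exposure for its ITO safety groups.
2. Split 'Treated with IMP' into first and repeat exposure in the recurrence-population efficacy, TEAE and immunogenicity summaries. Where a category has fewer than 5 participants, give listings, in line with SAP 2.4.4.9.1.
3. Relabel the ITO safety and six-monthly immunogenicity column as not treated in C301, and flag or list separately the patients first given caplacizumab in C302.
4. State whether C301 ADA results enter the categories for the PK and PD correlation.

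The cost is SAP wording, one derived variable and additional table columns; no new data are collected. The downside is small cells, and at 3% recurrence the split would yield listings only. A patient with several treated episodes can appear under both first and repeat exposure, which the tables should footnote.

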2.4.4.1 TTP-related events

The number and percentage of participants with TTP-related event as well as the number of such events, will be summarized. The total number and percentage of participants who have at least one of the TTP-related events will also be calculated.

For the ITO population, it will be after 12 months follow-up (M FU), 24M FU and 36M FU as well as a cumulative summary. For the Recurrence population, it will be during each recurrence period separately.

TTP-related events will be listed.

The time to the first TTP-related event will be summarized on the ITO population, using Kaplan-Meier (KM) estimates such as the median, 25% percentile and 75% percentile with associated 95% CIs, as well as the number of events and the number of censored observations. The KM estimates will also be presented graphically.

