1. INTRODUCTION

1.1. THROMBOTIC THROMBOCYTOPENIC PURPURA

Acquired thrombotic thrombocytopenic purpura (TTP) is a rare, potentially life-threatening, (sub)acute onset thrombotic microangiopathy (TMA) that leads to microvascular occlusions and variable organ ischemia throughout the body including brain, heart and to lesser extent kidneys. It is characterized by thrombocytopenia, hemolytic anemia and signs and symptoms of tissue ischemia, resulting from ultra-large von Willebrand factor (ULvWF) forming platelet aggregates in the microvasculature. Episodes are associated with significant mortality and morbidity acutely and may result poorer long term outcomes [1, 2]. In the longer term, patients with acquired TTP are at risk of recurrence of disease [3]. Reported recurrence rates vary considerably. Among patients followed for at least six months, the median incidence of recurrence was 18% (3-84%). The highest incidence (84%) occurred in the study with the longest mean follow-up (FU) time (13 years) [3]. The risk for recurrence seems to be the highest in the first year [4]. Frequent relapses may promote continuous damage from ongoing or intermittent episodes of endothelial injury, platelet dysfunction, and microvascular thrombosis [5]. Residual damage from the initial TMA-induced microvascular thrombotic event may mediate the subsequent development of vascular disease. Moreover, recent reports have suggested that survivors of an acute TTP episode are at risk for longer-term complications (e.g., a high incidence of hypertension, renal insufficiency, persistent cognitive deficits, depression, poorer quality of life and premature death) [1, 3, 6-9].

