3.6.4. EVALUATION OF EFFICACY PARAMETERS

The following efficacy analyses will be performed:

- TTP-related events (defined as TTP-related death, recurrence of TTP or reported major thromboembolic event [e.g., myocardial infarction, cerebrovascular accident, pulmonary embolism or deep venous thrombosis]):
 - Summary of the (cumulative) proportion of subjects with TTP-related events over time (including after 12M FU visit, after 24M FU visit, and after 36M FU visit), as well as the number of such events.
 - Summary of the time to first TTP-related event (starting from screening/baseline visit), based on a Kaplan-Meier (KM) analysis.
- Mortality: mortality rate during the study.
- Recurrence of disease:
 - Summary of the (cumulative) proportion of subjects with recurrence of disease over time (including after 12M FU visit, after 24M FU visit, and after 36M FU visit), as well as the number of such events.
 - Summary of time to first recurrence (starting from end of previous TTP episode), based on a KM analysis.
 - Summary of TTP recurrence information, including duration of daily PE.
 - Descriptive analysis of incidence of recurrence in relation to ADAMTS13 levels after previous TTP episode.
- Reported major thromboembolic events (e.g., myocardial infarction, cerebrovascular accident, pulmonary embolism or deep venous thrombosis):
 - Summary of the (cumulative) proportion of subjects with reported major thromboembolic events over time (including after 12M FU visit, after 24M FU visit, and after 36M FU visit), as well as the number of such events.
 - Summary of the time to first reported major thromboembolic event (starting from screening/baseline visit), based on a KM analysis.
- Cognitive assessment:
 - Summary of RBANS cognitive assessment score, including change from baseline, over time.
 - Descriptive comparison of RBANS cognitive assessment score with reference population.
- Quality of life assessment:
 - Summary of HIT-6 scores, including change from baseline, over time.
 - Summary of SF-36 scales, including change from baseline, over time, and at the end of recurrence period.

All efficacy endpoints related to assessments on the Q6M FU visits will be analyzed using the ITO population. Summarization will be conducted on the total study population and by analysis group. For the group-wise analysis, the following groups will be considered:

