2.4 STATISTICAL METHODS

For continuous parameters, descriptive statistics will be presented when $n \geq 2$. When $n = 1$, only sample size (n) and mean, i.e. the value itself, are shown. Descriptive statistics will include the number of non-missing data points (n), the arithmetic mean, the standard deviation (SD) (for baseline summaries) or standard error (SE) (for post-baseline, change from baseline, or percentage change summaries), the median, minimum and maximum.

For categorical parameters, frequency tabulations are prepared, consisting of frequency counts (non-missing observations) and percentages. Missing values will not be included in the denominator count when computing percentages.

Descriptive statistics of PK concentrations and PD data will additionally include 5% and 95% percentiles, SD of arithmetic mean, coefficient of variation (CV)% of arithmetic mean, geometric mean and geometric SD.

For the graphs showing mean values or percentages, an SE flag will be shown. For PK graphs showing geometric mean values, a geometric SD flag will be shown.

- Change from baseline and percentage change from baseline
- The change from baseline will be calculated for all post-baseline time points as:
- Change from baseline at time point $t = \text{value at time point } t - \text{baseline value}$.
- Percentage change from baseline at time point $t = 100 * \frac{[\text{value at time point } t - \text{baseline value}]}{\text{baseline value}}$.
- Change from baseline and percentage change from baseline will be calculated separately for each of the analysis periods from their respective baseline values.

Relative number of days

The relative day (DY) is calculated as follows:

- Visit date – reference date + 1 day, when the visit date is on or after the reference date
- Visit date – reference date, when the visit date is before the reference date.

The reference date is the date of first intake of the study drug, which by definition has DY=1. There is no DY=0.

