2.4.4.3 Recurrence of TTP

The number and percentage of participants with a recurrence of TTP as well as the number of such events, will be summarized over time for the ITO population (after 12M FU, 24M FU and 36M FU).

Time to the first recurrence of TTP will be summarized on the ITO population, using Kaplan-Meier (KM) estimates such as the median, 25% percentile and 75% percentile with associated 95% CIs, as well as the number of events and the number of censored observations. The KM estimates will also be presented graphically.

A subgroup analysis of incidence of recurrence of TTP to ADAMTS13 levels ($\geq 10\%$, $< 10\%$) after end of previous TTP episode in the ALX0681-C301 trial will be performed on the ITO population.

2.4.4.4 TTP recurrence information.

TTP recurrence information will be summarized for the recurrence population.

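### The 12-, 24- and 36-month event percentages have no stated denominator and no adjustment for censoring, so dropout biases them low or high depending on a choice the SAP leaves open

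*SAP*

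**What the plan says.** The protocol synopsis (Statistics) lists the proportions with TTP-related events, recurrence and major thromboembolic events among its main endpoints. Protocol 3.6.4 asks for a "Summary of the (cumulative) proportion of subjects with TTP-related events over time", including after the 12-, 24- and 36-month visits, and separately for a Kaplan-Meier (KM) summary of time to first event.

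SAP 2.4.4.1 implements the first part as "The number and percentage of participants with TTP-related event as well as the number of such events, will be summarized". On timing, it adds for all enrolled subjects: "it will be after 12 months follow-up (M FU), 24M FU and 36M FU as well as a cumulative summary". SAP 2.4.4.2 follows the same pattern. SAP 2.4.4.3 also gives counts and percentages for recurrence at the three visits, without a separate cumulative summary.

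Two general rules bear on the denominator. SAP 2.4 says "Missing values will not be included in the denominator count when computing percentages". SAP 2.4.4 says "no missing data imputation will be applied, and all efficacy endpoints will be analyzed as observed". The ITO population (SAP 2.3.1) is everyone enrolled.

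Time to first event is summarized "using Kaplan-Meier (KM) estimates such as the median, 25% percentile and 75% percentile", with 95% CIs, numbers of events and censored observations, and a graph. Event-free patients are censored at the end of the study (SAP 2.1.3.5.2, 2.1.3.5.5, 2.1.3.5.6). Protocol 3.1.1 defines the end of the study as the last visit of the last subject. SAP 2.1.4 defines it as the last protocol planned visit.

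**The concern.** A plain percentage at a fixed time estimates the risk to that time only if every subject without an event was followed that far. The plan foresees that some will not be. Protocol 3.2.4.1 ends all visits after loss to follow-up or withdrawal of consent, and SAP 2.2 defines loss to follow-up.

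In the group-wise analyses, subjects are evaluated only up to their first recurrence (SAP 2.4.4). For major thromboembolic events, observation is therefore cut short by design even without dropout. A group with more recurrences has less time in which such an event can be counted.

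At stake are the three-year event rates that readers will quote, and the descriptive contrast between the former caplacizumab and placebo groups. If follow-up differs between the groups, part of that contrast may reflect follow-up and not disease.

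**Working it through.** The documents give no planned event rate, dropout rate or C302 sample size, so there is no figure to reproduce. The inputs below are assumptions, with their sources where there are any.

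**Model.** Constant event hazard and independent constant dropout hazard over three years. F is the true 36-month risk and D the 36-month dropout. Per three years, l = −ln(1−F) and m = −ln(1−D).

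- All enrolled in the denominator: A = l/(l+m) × [1 − (1−F)(1−D)]
- Event-free dropouts removed: B = A / [A + (1−F)(1−D)]
- KM with dropouts censored at last contact estimates F.

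**Worked case, F = 30%, D = 25%.** l = 0.3567, m = 0.2877, l/(l+m) = 0.5535, and (1−F)(1−D) = 0.70 × 0.75 = 0.525.

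- A = 0.5535 × 0.475 = 0.263
- B = 0.263 / (0.263 + 0.525) = 0.334

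**36-month results**

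| True risk | Dropout | A: all enrolled | B: event-free dropouts removed |
|---|---|---|---|
| 30% | 15% | 27.8% | 31.9% |
| 30% | 25% | 26.3% | 33.4% |
| 30% | 40% | 23.8% | 36.2% |
| 18% | 20% | 16.2% | 19.8% |
| 18% | 40% | 14.2% | 22.4% |

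With no dropout, both equal the true risk.

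**12 months.** With F = 30% and D = 40%, the true risk is 11.2%, A is 10.3% and B is 12.1%. Each gap is about 0.9 points.

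**Group contrast.** Take two groups with the same 30% risk, one with 15% and one with 40% dropout. On basis A they differ by 27.8 − 23.8 = 4.0 points. On basis B they differ by 36.2 − 31.9 = 4.3 points in the opposite direction.

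**Do the KM quartiles fill the gap?** With complete follow-up, the 25th percentile is reached if at least n/4 subjects have events. C301 planned about 92 subjects (Protocol 1.2.4), so n = 50, 70 and 92 were tried.

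- At an illustrative 18% risk, the binomial probability of reaching the 25th percentile is 0.10, 0.07 and 0.06. The median is essentially never reached.
- At 30%, the 25th percentile is reached with probability 0.78, 0.82 and 0.88.

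The 18% is the median recurrence incidence in Protocol 1.1. It comes from studies with at least six months of follow-up and a range of 3 to 84%, so it is not a 36-month risk.

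**Does the KM curve fill it?** For TTP-related and thromboembolic events the clock starts at C302 baseline, and the analysis is on the ITO population. If censoring is at last contact, landmark values can be read from the curve. For recurrence, the clock starts at the end of the previous episode in C301, and anyone with a recurrence in C301 or between the studies is left out (SAP 2.1.3.5.5). Baseline may also be delayed until after site activation. That curve cannot give the risk from C302 baseline in the ITO population.

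**Censoring date.** If dropouts are carried event-free to a common end date, nobody is censored before 36 months, and 1 − KM(36) is simply events divided by all enrolled. That is basis A again.

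**The case against.** A reader might infer that the SAP counts dropouts as event-free and that the rates are therefore biased low. The documents do not say so. No denominator is stated, and the rules on missing values and as-observed analysis can be read as removing event-free dropouts, which reverses the bias. This objection stands: the direction is conditional. It does not save the percentages, because neither basis gives the true risk when there is dropout.

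A reader might also infer that the KM output is confined to quartiles. It is not. The list is introduced by such as, counts of events and censored observations are added, and the curve is drawn. Nor does the clock objection extend beyond recurrence. What remains is that no landmark probability, CI or number at risk is specified.

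On size, the dropout rates are assumed. At 18% risk the shortfall on basis A is 1.3 points with 15% dropout and 2.3 points with 25%. The quartile problem is serious near 18% but much smaller at 30%, so the two should not be quoted as though they came from one scenario.

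COVID-19 adds less than it may seem. SAP 2.5.3 extends visit windows and reports missed visits. A missed visit is not a lost event, since adverse events are collected to the last visit and every exacerbation or relapse is reported as serious (Protocol 3.4.9.1).

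Finally, the study is descriptive, with no formal test (SAP 2.4.4.8). The main endpoints are unranked, so nothing here makes these proportions primary. The crude percentage beside a separate KM summary also follows Protocol 3.6.4. These points limit the severity but do not remove the problem.

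**Conclusion.** The concern holds in a limited form and is worth correcting. The landmark percentages for all three endpoints have an undefined denominator and no adjustment for censoring. At an assumed 30% risk and 15 to 40% dropout, they would be off at 36 months by about 2 to 6 points in either direction, and by under 1 point at 12 months. These sizes rest on constant hazards, independent dropout and assumed dropout rates. If nearly everyone completes follow-up, the overall bias is negligible. The truncation at first recurrence in the group-wise thromboembolic analysis would still remain.

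The documents support neither a general claim of downward bias nor a claim that the KM output cannot help. For TTP-related and thromboembolic events, the planned curves can supply the landmark risks if dropouts are censored at last contact. For recurrence they cannot, because of the clock and the exclusions. The end-of-study censoring wording also needs settling. SAP 2.5.4 ends the observation period at the end of participation, which suggests that individual dates may be intended, but the endpoint definitions do not say so.

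**What to change.** - For TTP-related events, major thromboembolic events and recurrence, report 1 minus KM at 12, 24 and 36 months from C302 baseline, with 95% CIs and numbers at risk, in total and by analysis group. Where death competes with the event (for the composite, death not related to TTP), use cumulative incidence.
- For recurrence, add this C302-baseline analysis in the ITO population, and keep the planned KM from the end of the C301 episode as a separate result.
- In SAP 2.1.3.5.2, 2.1.3.5.5 and 2.1.3.5.6, replace censoring at the end of the study with censoring at the subject's own last contact. In the group-wise thromboembolic analysis, also censor at first recurrence.
- Keep the crude counts and percentages as supporting information, with the denominator stated at each landmark.

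The cost is SAP wording and a little more analysis; no new data collection is needed. The stated rates may move by a few points, in a direction that depends on the denominator that would otherwise have been used.
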